6.3 Management of sintilimab-related infusion reactions

Sintilimab may lead to severe or life-threatening infusion reactions, including severe hypersensitivity reactions or anaphylaxis. Signs and symptoms often occur during drug infusion or salvage therapy after infusion and usually resolve completely within 24 hours after infusion. Table 4 shows the management guidelines for sintilimab-related infusion reactions.

Table 3. Management guidelines for sintilimab-related infusion reactions

NCI CTCAE v4.03 grades	Treatment	pretreatment for subsequent doses
Grade 1: mild reaction; infusion interruption not indicated; intervention not indicated	Strengthen monitoring of vital signs based on the medical indications of the patient until the investigator deems that the subject's condition is stable.	None
Grade 2: Treatment or infusion interruption indicated, but	Stop infusion and monitor symptoms. Other appropriate drug treatments may include but are not limited to intravenous infusion, antihistamines, NSAIDs, paracetamol, anesthesia. Strengthen monitoring of vital signs based on the medical	The subject can receive the following pretreatment drugs 1.5 hours (\pm 30 minutes) before sintilimab infusion: 50 mg diphenhydramine (or

symptomatic treatment (such as antihistamines, non-steroidal anti-inflammatory drugs [NSAIDs], anesthesia, intravenous fluid supplementation) should be performed as soon as possible to enable rapid response; ≤24 hours of prophylactic drug use is indicated
	
indications of the patient until the investigator deems that the subject's condition is stable. If symptoms alleviate within 1 hour after drug infusion is stopped, the infusion can be restarted at 50% of the initial infusion rate (e.g., decrease from 100 mL/hr to 50 mL/hr). Otherwise, the drug will be interrupted until symptoms abate, and the subject should receive pretreatment before the next scheduled dose. For subjects who still develop Grade 2 toxicity after receiving sufficient pretreatment, further study treatment must be permanently discontinued.
	
equivalent dose of antihistamine), Oral administration of 500–1000 mg paracetamol (or equivalent dose of antipyretic)


Grade 3: Long duration (rapid response does not occur even after symptomatic treatment and/or temporary interruption of infusion); symptoms recur after initial improvement; inpatient treatment is required due to other clinical sequelae (such as kidney injury, lung infiltration) Grade 4: Life-threatening, vasopressor or ventilator support indicated
	
Stop infusion Other appropriate drug treatments may include but are not limited to: Adrenaline**, intravenous infusion, antihistamines, NSAIDs, paracetamol, anesthesia, Oxygen, vasopressor, corticosteroids. Strengthen monitoring of vital signs based on the medical indications of the patient until the investigator deems that the subject's condition is stable. Inpatient treatment may be indicated. **Adrenaline must be immediately administered if anaphylaxis occurs. Further investigational drug treatment will be permanently discontinued.
	
No subsequent treatment

The ward should be equipped with appropriate resuscitation equipment, and the physician should be contactable at any time during the dosing period. For further information, please refer to the Common Terminology Criteria for Adverse Events (CTCAE v4.03)(http://ctep.cancer.gov)
		

6.4 Dose modification for anlotinib

If the investigator confirms that toxicity is mainly caused by anlotinib, dose reduction for

anlotinib alone is acceptable. If toxicity caused by 2 or more drugs cannot be confirmed, dose reduction should be performed for all related drugs. If anlotinib dosing is delayed during treatment (3 weeks per cycle), all future dosing dates will be delayed to ensure that the dosing interval between anlotinib treatment cycles is 21 ± 3 days. The anlotinib cycles and sintilimab cycles will be synchronized as much as possible by adjustments of permissible time windows.

The adverse reactions caused by **anlotinib** can be managed with symptomatic treatment, drug discontinuation, and/or dose modification. It is recommended that the dose be adjusted under the physician's guidance according to the severity of the adverse reaction: ① First dose modification: 10 mg, qd; ② Second dose modification: 8 mg, qd. If a third dose modification is required, the drug should be permanently discontinued.

When on 8 mg doses, the dose can be increased to 10 mg if necessary, depending on the adverse reaction.

When a drug-related adverse reaction occurs, the general rules in Table 3 should be consulted for dose modifications. When adverse reactions such as abnormal liver function [including ALT elevation, AST elevation, or total bilirubin elevation], proteinuria, decreased platelet count, or a bleeding event occur, dose modification and management are performed according to the principles in Tables 4–7.

Table 3. General rules of anlotinib dose modification for various grades of adverse reactions

Adverse reaction grade	Dosing time	Dose modification principle
Grade 3	Drug interruption until adverse reaction resolves to grade <2	Subsequent doses are reduced by one level; If the patient does not recover after 2 weeks, consider permanent discontinuation of the drug.
Grade 4	Drug interruption until adverse reaction resolves to grade <2	Subsequent doses are reduced by one level. Consider permanent drug discontinuation if the patient does not recover after 2 weeks, or consider permanent drug discontinuation based on the physician's judgment.

Table 4. Dose modification principles and management recommendations in case of abnormal hepatic function

Adverse reaction grade	Dose modification principle	Management recommendations
Grade 2 (normal baseline)	Drug interruption. If AE resolves to grade <2 within 2 weeks, continue the drug treatment at a dose reduced by one level	Aggressive hepatoprotective treatment should be performed, and hepatic function is monitored once every week
Grade 2 (Abnormal baseline)	Continue drug treatment at the original dose	
Grade 3	Drug interruption. If AE resolves to grade <2 within 2 weeks, continue drug treatment at a dose reduced by one level	Aggressive hepatoprotective treatment should be performed, and hepatic function is monitored once every 2 weeks until toxicity restores to Grade <2 or can be explained by other reasons
Grade 4	Permanent drug discontinuation	Aggressive hepatoprotective treatment should be performed, and hepatic function is monitored 1–2 times every week until toxicity resolves to Grade <2 or can be explained by other reasons

Table 4. Dose modification principles and management recommendations in case of proteinuria

Adverse reaction grade	Dose modification principle	Management recommendations
Grade 2, routine urine protein test ++, but 24 h urine protein quantitation test result of 1.0 g–2.0 g (not including).	Maintain original dose	Aggressive symptomatic treatment should be provided, and a routine urine test is performed once every week
Grade 2, routine urine protein test ++ or above, but 24 h urine protein quantitation test result of 2.0g–3.5 g (not including).	Drug interruption If AE resolves to grade <2 within 2 weeks, continue drug treatment at a dose reduced by one level.	Aggressive symptomatic treatment should be performed, and the drug permanently discontinued if the AE occurs for a 3rd time.
Grade 3: 24 h urine protein quantitation test result of ≥3.5 g	Drug interruption If AE resolves to grade <2 within 2 weeks, continue drug treatment at a dose reduced by one level.	Aggressive symptomatic treatment should be performed, and the drug permanently discontinued if the AE occurs for the 3rd time.

Table 6. Dose modification principles and management recommendations for decreased platelet count

Adverse reaction grade	Dose modification principle	Management recommendations
Grade 2, platelet count of 50–75 × 10 ⁹ /L	Drug interruption. If AE resolves to grade <2 within 1 week, continue drug treatment at the original dose	A routine blood test is performed once every 2–3 days; in the subsequent dosing period, a routine blood test is performed once a week
	Drug interruption. If AE resolves to grade <2 within 2 weeks, continue the drug treatment at a dose reduced by one level	A routine blood test is performed once every 2–3 days; in the subsequent dosing period, a routine blood test is performed once a week
Grade 3, platelet count of 25–50 × 10 ⁹ /L	Drug interruption. If AE resolves to grade <2 within 2 weeks, continue the drug treatment at a dose reduced by one level.	A routine blood test is performed once every 2–3 days, and in the subsequent dosing period, a routine blood test is performed once a week
Grade 4: Platelet count of <25 × 10 ⁹ /L	Permanent drug discontinuation	A routine blood test is performed daily until AE resolves to Grade ≤2 and aggressive symptomatic treatment is performed

Table 7. Dose modification principles and management recommendations in bleeding events

Bleeding event	Dose modification principle	Management recommendations
Grade 2	Drug interruption. If AE resolves to grade <2 within 2 weeks, continue drug treatment at a dose reduced by one level	Aggressive symptomatic treatment should be performed
Grade ≥3	Permanent drug discontinuation	Emergency medical intervention should be performed

Drug administration in patients with hepatic or renal insufficiency:

There is no relevant data on the effects of anlotinib in patients with hepatic or renal insufficiency. Clinical studies have shown that long-term use could result in liver injury and proteinuria. It is recommended that this product be used with caution under the guidance of a physician based on clinical conditions and laboratory test results for patients with hepatic and renal insufficiency. This product is prohibited in patients with severe hepatic and renal insufficiency.

Strong CYP1A2 and CYP3A4/5 inhibitors (such as ciprofloxacin or ketoconazole) may increase the plasma concentration of this product. It is recommended that drugs with no or the lowest inhibitory effects on these enzymes should be selected as concomitant medications.

CYP1A2 and CYP3A4/5 inducers (such as omeprazole or rifampin) may decrease the plasma concentration of this product. It is recommended that drugs with no or the lowest inducing effects on these enzymes should be selected as concomitant medications.

6.5 Precautions for anlotinib

Bleeding: VEGFR inhibitor antineoplastic agents may increase the risk of bleeding. In clinical studies of anlotinib, this product increased the risk of hemoptysis. However, the clinician should be reminded to pay close attention to this risk.

This product should be used with caution in patients with coagulation abnormalities. Prothrombin time and international normalized ratio should be closely monitored when using this product. The drug should be interrupted if a Grade 2 bleeding event occurs, and drug treatment should be continued at a dose reduced by one level after AE resolves to Grade <2 within 2 weeks. The drug should be permanently discontinued if a Grade 3 or above bleeding event occurs.

Blood pressure increase: A blood pressure increase is the most common adverse reaction of this product. In clinical studies, it was observed that anlotinib could mildly to moderately increase blood pressure. This AE occurs 1 week after dosing and can normally be controlled with conventional antihypertensive medications. **Blood pressure should be monitored every day in the first 6 weeks of dosing.** Blood pressure should be periodically monitored in subsequent doses, and active communication with the physician is required when blood pressure increases. Conventional antihypertensive treatment can mostly control the blood pressure increase. An uncontrollable blood pressure increase can usually be relieved by dose reduction or discontinuation of this product.

If a blood pressure increase occurs, antihypertensive treatment or dose modification of this product should be performed under the guidance of the specialist. Drug interruption is recommended if a Grade 3/4 blood pressure increase occurs. If a Grade 3/4 blood pressure increase recurs after dosing is resumed, subsequent doses can be reduced by one level. Drug discontinuation is recommended if the adverse reaction persists. This product should be discontinued in patients who develop a hypertensive crisis.

Cardiotoxicity: It was observed in clinical studies that anlotinib could cause electrocardiogram abnormalities, including a prolonged QT interval. The drug should be used with caution in patients with a known medical history of a prolonged QT interval (QTc \geq 480

ms). In patients on anlotinib who take antiarrhythmic drugs or have related underlying heart disease, bradycardia, and electrolyte disturbance, electrocardiography should be performed every 2–3 weeks to evaluate the QT interval.

Electrocardiography and cardiac function should be closely monitored during the dosing period. Drug interruption is recommended if a Grade 3/4 adverse reaction occurs. If a Grade 3/4 adverse reaction recurs after dosing is resumed, subsequent doses can be reduced by one level. Drug discontinuation is recommended if the adverse reaction persists. Drug discontinuation is recommended for patients who develop Grade III–IV heart failure or patients with a left ventricular ejection fraction <50% on Doppler echocardiography.

Stroke risk: Although a stroke event has yet to be observed in existing clinical trials of anlotinib, hypertension and hyperlipidemia are common adverse reactions of anlotinib and constitute a high-risk factor for stroke. Long-term use of this product may increase stroke risk. Therefore, it is recommended that blood pressure, blood lipids, and other stroke risk factors should be closely monitored in high-risk stroke patients to prevent stroke.

Epilepsy: Epilepsy was observed in patients in the anlotinib arm in clinical trials. It has not been confirmed whether this product can cause epilepsy or increase the risk of epilepsy. This product should be used with caution under the guidance of a physician for patients with a medical history of epilepsy.

Dermatotoxicity: Hand-foot-skin reaction (swelling and pain in the palms and soles or erythema of the fingers and toes) is a common adverse skin reaction with this type of drug. A Grade 1 hand-foot-skin reaction is characterized by painless mild skin changes or dermatitis (e.g., erythema, edema, hyperkeratosis); a Grade 2 hand-foot-skin reaction is characterized by painful skin changes (e.g., desquamation, blisters, bleeding, swelling, and hyperkeratosis) and affects instrumental activities of daily living; a Grade 3 hand-foot-skin reaction is characterized by severe skin changes (e.g., desquamation, blisters, bleeding, swelling and hyperkeratosis) and accompanied by pain, which affects activities of daily living.

For patients with a Grade 1 hand-foot-skin reaction, observation is continued, and supportive treatment is not required. For a Grade 2 or above hand-foot-skin reaction, symptomatic treatment should be considered, including enhancing skin care, maintaining skin cleanliness, and avoiding secondary infection; pressure or abrasion should be avoided; use of a moisturizer or lubricant and topical application of urea- and corticosteroid-containing lotions or lubricants are recommended; topical antifungal or antibiotic treatment could be adopted when necessary.

If a Grade ≥ 3 hand-foot-skin reaction occurs, subsequent doses can be reduced by one level (see [Administration Method and Dosage]). Drug discontinuation is recommended if the adverse reaction persists.

Hypothyroidism: Baseline thyroid function tests are recommended, and patients with hypothyroidism should receive the corresponding standard treatment before treatment with this product. All subjects should be closely monitored for signs and symptoms of hypothyroidism while on treatment. Thyroid function tests should be performed for patients with signs and symptoms of hypothyroidism, and corresponding standard treatment should be provided.

Proteinuria: Proteinuria is a common adverse reaction of anlotinib. In clinical studies, it was observed that oral administration of anlotinib could induce proteinuria. Anlotinib should be used with caution, and close monitoring is required for patients with renal insufficiency. It is recommended that periodic routine urine tests be performed. A 24 h urine protein measurement should be performed for patients with 2 continuous $\geq++$ urine protein results. Dose interruption, dose modification, and permanent drug discontinuation should be performed based on the severity of the adverse reaction.

Hyperlipidemia: During clinical trials, the anlotinib group had more severe hyperlipidemia. Patients with hyperlipidemia should switch to a low-fat diet. For patients with Grade 2 or above hypercholesterolemia (≥ 7.75 mmol/L) or Grade 2 or above hypertriglyceridemia [$\geq 2.5 \times$ ULN], HMG-CoA reductase inhibitor (atorvastatin, etc.) or a suitable lipid-lowering drug should be used.

Hepatotoxicity: In clinical studies, it was observed that oral administration of anlotinib could induce transient transaminase elevation or total bilirubin elevation. This product should be used with caution in patients with underlying serum transaminase and total bilirubin elevations. Studies have not been performed in patients with hepatic insufficiency; therefore, anlotinib should be used with caution. Close monitoring is required for patients with a medical history of hepatic insufficiency (hepatic function be tested once within the first 3 weeks of drug administration). This drug is prohibited in patients with severe hepatic insufficiency. Drug interruption is recommended if a Grade 3/4 transaminase and total bilirubin elevation occurs. At the same time, serum transaminase and total bilirubin should be monitored until their levels significantly decrease before resuming dosing. If a Grade 3/4 adverse reaction recurs after dosing is resumed, subsequent doses can be reduced by one level. Drug discontinuation is recommended if the adverse reaction persists.

Diarrhea: Product absorption may be affected if taken by patients with diarrhea. Therefore, diseases causing diarrhea should be actively treated. This product can be taken under the guidance of the physician after improvement. Drug interruption is recommended if Grade 3/4 diarrhea occurs when taking this product. If Grade 3/4 diarrhea recurs after dosing is resumed, subsequent doses can be reduced by one level. Drug discontinuation is recommended if the adverse reaction persists.

Wound healing complications: Studies of the effects of anlotinib on wound healing have yet to be conducted. In clinical studies, patients with unhealed wounds from major

surgeries within the past 4 weeks were excluded. Since there is limited evidence on when the patients can take anlotinib after surgery, it is recommended that this product be temporarily discontinued before surgery and for 30 days after surgery.

Effects on driving and machinery operation: Fatigue may occur during dosing. Patients should pay attention when driving or operating machinery.

7. Concomitant Treatment

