Inclusion criteria	
 1. Women aged > 18 years; 2. Histologically confirmed endometrial cancer; 3. Recurrent or advanced endometrial cancer with at least one treatment with systemic platinum-based chemotherapy; 
 • Low probability of cure for recurrent endometrial cancer with surgery and/or radiotherapy and failure of at least one systemic platinum-based chemotherapy after recurrence. • Newly diagnosed advanced endometrial cancer persisting after standard treatment with surgery ± radiochemotherapy and at least one systemic platinum-based chemotherapy. 4. Objectively measurable lesions based on Response Evaluation Criteria In Solid Tumors (RECIST 1.1) and at least one target lesion; 
 • In principle, lesions in the field of previous radiotherapy are considered non-target unless there is radiological evidence of progression or a biopsy with progression within 90 days after radiotherapy. 5. Eastern Cooperative Oncology Group (ECOG) score of 0–2; 6. Expected survival >3 months; 7. Major organ function fulfilling the following criteria (correction of the following parameters and supportive treatment are permitted one week before enrollment);

	
 • Absolute neutrophil count $\geq 1.5 \times 10^9/L$, platelet count $\geq 70 \times 10^9/L$, hemoglobin ≥ 80 g/L • Alanine transaminase (ALT) and aspartate transaminase (AST) ≤ 2.5 times upper limit of normal (ULN) (< 5 times for patients with liver metastases) and total bilirubin ≤ 1.5 times ULN • Serum creatinine ≤ 1.5 times ULN • International normalized ratio (INR) < 1.5 times ULN • Proteinuria $\leq (+)$ • Thyroid-stimulating hormone (TSH) ≤ 1 time ULN (measure FT3 and FT4 if TSH abnormal; subjects with normal FT3 and FT4 can be enrolled) 
8. Voluntarily signed informed consent form.

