Hepatitis B, hepatitis C test ¹⁰	X				If positive, hepatitis B DNA and hepatitis C RNA will be measured on d1 ± 7d in every 2 cycles					
HIV test ¹⁰	X									
Pregnancy test ¹¹	X									

12-lead electrocardiogram		X			X			X	X	
Clinical evaluation examination										
ECOG scoring	X				X					
Evaluation of adverse events ¹²	From the signing of the informed consent form to 30 days after the last dose									
Quality of life questionnaire ¹³		X			X ⁸				X	
Administration of investigational product										
IBI308 administration		X			X					
Anlotinib administration	Administration is recorded daily on d1–d14 of every treatment cycle									
Efficacy evaluation										
Radiologic tumor evaluation ¹⁴	X	Evaluation is performed once after the 2nd treatment cycle (C3) and once after the 4th treatment cycle (C5). Subsequently, an evaluation will be performed once after the 7th cycle (C8) and once after the 10th cycle (C11). After the 10th cycle, an evaluation will be performed once every 4 treatment cycles, and the time window for radiological evaluation is ± 7 days.								
Follow-up after treatment has ended										

Progressive disease	Radiologic evaluation is performed every 3 months after the last dose until disease progression						
Biomarker exploration							
Biomarker blood sampling/sample collection	X						

1. The informed consent form should be signed by subjects before any procedures outlined in the protocol.
2. Vital signs include body temperature, pulse, respiratory rate, and blood pressure.
3. Height is only measured during the screening period. Weight is measured before every dose, except for physical examination during the screening period; physical examination abnormalities during the trial only need to be recorded in the CRF.
4. Routine blood tests include RBC, HGB, HCT, WBC, PLT, and white blood cell categories [LYM, ANC, MONO, EOS, BASO].
5. Blood chemistry includes liver function tests [TBIL, ALT, AST, γ -GT, ALP, ALB, TP, LDH], renal function tests [UREA, Cr], blood electrolytes [Na, K, Cl, Mg], amylase, lipase, blood lipids [total cholesterol (CHO), triglycerides (TG), high-density lipoprotein cholesterol, low-density lipoprotein cholesterol], and fasting blood glucose.
6. Routine urine tests include UWBC, UPRO, URBC, UGLU. Any subjects with $\geq 2+$ proteinuria in routine urine tests must undergo 24-hour urine protein quantification during the screening period.
7. Routine stool test should include stool routine.

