4.1 Inclusion criteria

- (1) Women aged > 18 years;
- (2) Histologically confirmed endometrial cancer;
- (3) Recurrent or advanced endometrial cancer with at least one treatment with systemic platinum-based chemotherapy;
 - Low chance of a cure for recurrent endometrial cancer with surgery and/or radiotherapy and failure of at least one treatment with systemic platinum-based chemotherapy after recurrence.
 - Newly diagnosed advanced endometrial cancer persisting after standard treatment with surgery \pm radiochemotherapy and at least one treatment with systemic platinum-based chemotherapy.
- (4) Objectively measurable lesions based on RECIST 1.1 criteria and at least one target lesion;

- In principle, lesions in the field of previous radiotherapy are considered as non-target lesions unless there is radiological evidence of progression or a biopsy with progression within 90 days after radiotherapy.
- (5) Eastern Cooperative Oncology Group (ECOG) score of 0–2;
- (6) Expected survival >3 months;
- (7) Major organ function fulfills the following criteria (correction of the following parameters and supportive treatment are allowed 1 week before enrollment);
 - Absolute neutrophil count $\geq 1.5 \times 10^9/L$, platelet count $\geq 70 \times 10^9/L$, hemoglobin $\geq 80g/L$
 - Alanine transaminase (ALT) and aspartate transaminase (AST) $\leq 2.5 \times$ upper limit of normal (ULN) ($<5 \times$ for patients with liver metastases) and total bilirubin $\leq 1.5 \times$ ULN
 - Serum creatinine $\leq 1.5 \times$ ULN
 - International normalized ratio (INR) $<1.5 \times$ ULN
 - Proteinuria $\leq (+)$
 - Thyroid-stimulating hormone (TSH) $\leq 1 \times$ ULN (measure FT3 and FT4 if TSH abnormal; subjects with normal FT3 and FT4 can be enrolled)
- (8) Voluntarily signed informed consent form.

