- Blood routine/blood biochemistry/urine routine/stool routine (within 3 days before the 1st dose);
- Coagulation function tests (within 3 days before the 1st dose);
- Pregnancy test;
- Thyroid function test;
- HIV antibodies, Hepatitis B-five test (HBsAg, HBsAb, HBcAb, HBeAg, HBeAb) and HBV-DNA (if the subject is positive for HBsAg and HBeAg), HCV antibody and HCV-RNA (if the subject is positive for HCV antibody);
- Evaluation of adverse events;
- Radiologic tumor evaluation;
- Pathology consultation
- Archived or fresh tumor tissue samples (non-essential).

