8.2 Test items during the treatment period

- Physical examination: weight, vital signs, ECOG scoring once before each dose;
- 12-lead electrocardiography;
- Blood routine (3 days before dosing in every treatment course and once a week during treatment, the number of tests can be increased if $WBC < 3.0 \times 10^9/L$, $N < 1.5 \times 10^9/L$, $Hb < 80g/L$, $PLT < 75 \times 10^9$).
- Blood biochemistry (3 days before dosing in every treatment course);
- Stool and urine test (3 days before dosing in every treatment course);
- Coagulation function test (3 days before dosing in every treatment course);

- Tumor markers (should at least include CA125, CA199, and HE4): tested once before dosing in every treatment course until tumor progression or when the investigator deems it necessary to increase the number of tests;
- Thyroid function test once before dosing in the 1st and 2nd treatment courses and once every 3 treatment courses thereafter;
- HBV-DNA and/or HCV-RNA (if applicable, once every 2 cycles);
- Adverse event evaluation (closely monitored items during drug administration include blood pressure abnormalities, hand-foot-skin reaction, nausea, vomiting, diarrhea, fever, and fatigue). Grading is performed according to CTCAE v4.03.
- Recording of concomitant medications;
- Radiologic tumor evaluation (see Table 1 for details)
 - Administration of investigational drug;
 - Quality of life evaluation.

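### Section 6.5 calls for 24-hour urine protein after two consecutive ++ results, but the section 6.4 table needs that value to act on the first one

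*Protocol*

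**What the plan says.** Four parts of the protocol deal with urine protein on treatment.

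- **Section 6.4** sends proteinuria to its own dose table (the second of two tables numbered 4). The first row reads "Grade 2, routine urine protein test ++, but 24 h urine protein quantitation test result of 1.0 g–2.0 g (not including"), and the dose is kept. The second row, also Grade 2, is ++ or above with 2.0 g to below 3.5 g, and the drug is interrupted. The third row is Grade 3, at least 3.5 g in 24 hours, again with interruption.
- **Section 6.5**, under Proteinuria, says "A 24 h urine protein measurement should be performed for patients with 2 continuous" results of ++ or more. It also recommends periodic urine tests, without an interval.
- **Section 8.2** schedules the routine test: "Stool and urine test (3 days before dosing in every treatment course").
- **Section 6.1** requires other toxicities to be back to Grade 0–1 or baseline before each Day 1 dose. It excepts, among others, cases covered by special rules in the protocol and conditions that the investigator judges not clinically significant.

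At screening, Table 1 note 6 says that a subject with 2+ or more "must undergo 24-hour urine protein quantification during the screening period". Inclusion criterion 7, in the synopsis and in section 4.1, limits proteinuria to (+). The same criterion adds "correction of the following parameters and supportive treatment are permitted one week before enrollment".

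**The concern.** The dose table can be applied only when a 24-hour value is available, and the instruction that produces the value comes one ++ result too late. An investigator who follows the text after a first ++ has no basis for choosing between continuing and interrupting anlotinib, and cannot recognise Grade 3.

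The protocol itself calls proteinuria a common reaction to anlotinib, and the incidence of adverse events is a secondary objective (section 2.2). At stake are a dosing decision and the consistency with which the grade and onset of proteinuria are recorded. In the two interruption rows, permanent discontinuation depends on a third occurrence, so an episode that was never quantified may also be missed in that count.

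**Working it through.** The plan states no figure to reproduce. The check is a comparison of the texts, plus one interval.

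**1. What the table needs.** The rows are 1.0 to <2.0 g (keep dose), 2.0 to <3.5 g (interrupt) and ≥3.5 g (Grade 3, interrupt). The dipstick does not separate them: ++ fits both Grade 2 rows, and the Grade 3 row mentions no dipstick result. Calling a ++ Grade 2 does not settle the matter, because Grade 2 carries both actions.

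**2. What would produce the value after a first ++ on treatment.**
- Section 6.5: not triggered, since it asks for two consecutive results.
- Table 1 note 6: not triggered, since it covers the screening period.
- Section 8.2 and Table 1: routine urine once per course, with no 24-hour test.
- Weekly urine testing: appears only in the 1.0–2.0 g row, so it starts only after the missing value is known. This is circular.

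No rule in the document closes the gap.

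**3. Whether section 6.1 settles it.** The scheduled urine test falls just before Day 1, when the Grade 0–1 requirement applies. Keeping the dose in the 1.0–2.0 g row may be one of the special protocol rules that section 6.1 excepts. Whether that row applies depends on the same missing value.

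**4. Length of the delay.** Inputs: a dosing interval of 21 ± 3 days between anlotinib cycles (section 6.4) and dosing on days 1–14 (section 5.2). Assume that the second ++ comes from the next scheduled test, taken at the same point before Day 1:

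- shortest: 21 − 3 = 18 days
- longest: 21 + 3 = 24 days
- anlotinib given in between, if dosing continues: one course of 14 days

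An unscheduled repeat would shorten this; the protocol neither requires nor forbids one.

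**5. Screening.** A dipstick of 2+ or more exceeds the (+) limit in both criteria lists. Note 6 then requires a 24-hour test but gives no gram limit and no consequence for entry. It may serve the one-week correction allowance, but the protocol does not say so.

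**The case against.** The best defence is that the passages form a sequence: two ++ results, then the 24-hour test, then the table. The table states no trigger of its own, section 6.5 is a precautions section written in the style of a product label, and section 6.4 points to the tables for management. Nothing forbids an earlier test. The pre-dose check in section 6.1 may also hold back a patient with unresolved toxicity.

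This is fair as far as it goes, but the sequence gives no action for the first ++. The table describes a single ++ and attaches opposite instructions to it, and the section 6.1 check turns on the same unmeasured value.

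The defence does succeed against several stronger readings that a reader might infer:

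- *Three competing triggers.* Note 6 covers screening and section 6.5 covers patients on anlotinib, so a difference between them is not a contradiction. That the table requires the test at any ++ is an inference from its rows.
- *Eligibility depends on the page.* Both criteria lists give the same (+) limit, and note 6 offers no alternative. It is an unexplained test, not a second entry rule. Nothing in the text shows that patients would be wrongly enrolled and later removed under section 4.3.
- *The grade depends on the page.* The gram cut-offs stand in one table only. What varies is whether and when the value is obtained.
- *Adverse events will be under-graded.* The grading standard is CTCAE v4.03, which is not reproduced in the protocol, so whether a lone ++ can be graded under it cannot be judged here.
- *A safety rate shifts by a known amount.* One patient in 23 is 1/23 = 4.3 percentage points, but that is true of any adverse event and says nothing about how often this one would arise.

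**Conclusion.** The point holds in a limited form. Followed as written, the protocol leaves a first on-treatment ++ without a place in the table that decides whether anlotinib continues, and leaves it unclear whether the section 6.1 requirement or its exception governs the next dose.

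The 18 to 24 days and the intervening 14-day course rest on the assumptions that the second result comes from the scheduled test and that dosing continues meanwhile. The number of patients affected cannot be derived from the document. The reach is anlotinib dose decisions and the recorded grade and timing of proteinuria. Grade cut-offs, the response endpoint, the sample size and the Simon boundaries do not change. Note 6 is a secondary gap in explanation.

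**What to change.** Reconcile Table 1 note 6, section 6.1, the proteinuria table in section 6.4 and the Proteinuria paragraph of section 6.5. The on-treatment trigger should yield a 24-hour value by the time the table has to be applied, and the text should say how the pre-dose requirement in section 6.1 applies while that value is pending. In note 6, state what role, if any, the screening 24-hour result has in eligibility under inclusion criterion 7. Which trigger and which threshold apply is for the investigators to decide.

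The cost is wording in a few places. The 24-hour test is already in the protocol, so the added burden is at most a few more collections.
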